7.4 Missing data

Subjects missing data values will not be excluded from the analysis, but their data will not be replaced; frequency of missing data will be given for all analysed variables.

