		
alcohol use.
 
Subject will be screened for the following STIs during the enrolment visit: HIV, syphilis, hepatitis A/B/C, Chlamydia trachomatis, Neisseria gonorrhoea, and Mycoplasma genitalium.
 
Participants will be asked to return approximately one week later to discuss their HIV result and whether they wish to proceed with initiation of PrEP.
 
The decision regarding initiation of continuous or intermittent PrEP is based on a discussion with the subject and study team (doctor/nurse), subjects' personal preference, medical considerations and whether the expected use will surpass more than 15-20 tablets of FTC/TDF per month.
 
HIV testing will be repeated at 2, 4 and 8 weeks from the most recent high risk exposure (for HIV acquisition) prior to initiation of PrEP. Thereafter participants are requested to visit the clinic every 3 months from PrEP initiation (for the next 24 months) for HIV & STI testing, evaluation of compliance (blood test for drug monitoring in continuous PrEP arm, drug diaries in both continuous and intermittent PrEP arms), assessment of clinical and/or biochemical adverse reactions and quality of life and sexual behaviour assessment. Subjects will be asked to answer the same questions regarding sexual behaviour and quality of life at follow up visits as at inclusion study visit.

Statistics	Sample size	Not applicable
	Methods	Categorical variables will be described by means of absolute and relative frequencies, while continuous variables by means of mean, standard deviation, quartiles, min and max.

LIST OF ABBREVIATIONS

AE	Adverse Event
ART	Anti retroviral therapy
COHP	Country of high prevalence of HIV
CRA	Clinical Research Associate
CRF	Case Report Form
CSR	Clinical Study Report
CT	Chlamydia trachomatis
DM	Data Manager
EC	Ethics Committee
eCRF	Electronic Case Report Form
EDC	Electronic Data Capture
EMA	The European Medicines Agency
GCP	Good Clinical Practice
HIV	Human Immunodeficiency Virus
ICF	Informed Consent Form
ICH	International Conference on Harmonisation
IMP	Investigational Medicinal Product
ISF	Investigator Site File
ITT	Intention-To-Treat
MG	Mycoplasma genitalium
MSM	Men who have sex with men
NG	Neisseria gonorrhoea
PI	Principal Investigator
PIS	Patient Information Sheet
PrEP	Pre-Exposure Prophylaxis
SAE	Serious Adverse Event
SD	Standard Deviation
SDV	Source Data Verification
SUSAR	Suspected Unexpected Serious Adverse Reaction
STI	Sexually Transmitted Infections

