3 POPULATION

3.1 Inclusion Criteria

In order to participate in the PrEP arm of this study the subjects must meet all of the following inclusion criteria:

1. Male, female or transgender persons aged ≥ 18 years who are offered or have started PrEP in routine clinical practice, and 2, 3, 4, 5, 6 or 7 (below).
2. Men who have sex with men (MSM) and transgender persons;
 - a. who have had unprotected anal sex with two or more partners during the last six months and/or
 - b. who have had bacterial sexually transmittable infection(s) during the last twelve months and/or
 - c. who have used post-exposure prophylaxis(PEP) during the last twelve months and/or
 - d. who use recreational drugs when having sex
3. Indication for PrEP is present according to the assessment of the health care provider
4. Men and women who are at high risk of HIV according to their sexual practices
5. HIV-negative partner of a HIV-positive person not yet virologically suppressed by antiretroviral therapy (ART)
6. Sex workers with inconsistent condom use
7. Persons with inconsistent condom use with sexual partners in / from countries with a high prevalence of HIV (COHP)

Subjects who are included in the PrEP arm will act as their own controls regarding possible changes in psychological and sexual health. At the screening visit they will complete questionnaire requesting information related to last 6 months prior to study start. Individuals who seroconvert during the observational period will be transferred to the out-patient clinic for Infectious Diseases as is already standard of care.

Patients diagnosed with HIV in general clinical practice and referred to the out-patient clinic at the Dept. of Infectious Diseases, OUS, will be asked to act as controls to assess their past psychological and sexual health. They will be asked to sign the consent form and answer the same questionnaire as those in the PrEP arm but not followed further in this study.

Frequency of STI reported to the National Institute of Public Health (MSIS) will be compared with the frequency of STIs in the study cohort.

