4 TREATMENT PROCEDURES

4.1 Study plan

The observation will begin after the subjects have signed the informed consent form. PrEP treatment should then be initiated when the HIV antibody/antigen test (4th generation test) taken at the first visit is confirmed negative.

However, the window period to rule out HIV infection is 12 weeks. It is not desirable that participants are undergoing HIV seroconversion when they commence PrEP, however the study population is per definition at high-risk for HIV acquisition. It is likely that the majority of the participants will not be in a position to abstain from sex or use condoms effectively for a 12 week period. Therefore it is NOT recommended to delay PrEP pending a negative HIV test results 12 weeks from the last high risk exposure. International and national guidelines do not recommend delaying PrEP initiation in this high risk group for HIV acquisition. Per definition, those in need for PrEP are at high risk for HIV acquisition justifying PrEP initiation even at first visit.

For those who have had high risk exposure within 14 days prior to screening, a HIV-DNA provirus test should be requested and the serum test for HIV should be repeated at 2 weeks, 4 weeks and 8 weeks and 12 weeks from the day they commenced PrEP.

Subjects that have already commenced PrEP treatment can be included in the study. These subjects will be requested to consent to collection of historical medical information from the date when the PrEP treatment was initiated.

Follow-up visits are according to clinical practice, clinical judgement and standard patient management described in SmPC. For those outside the window period for HIV infection a standard visit at 4 weeks and 12 weeks post initiation of PrEP and thereafter every 3 months during the PrEP treatment for 24 months. Where clinically indicated the subject may attend the clinic between 3 months' follow-up visits. Data from these visits will be collected as Extra Clinical Visits.

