7.2 Study Populations

Data will be described on enrolled subjects undergoing PrEP treatment. Subjects who do not satisfy inclusion criteria will not be included in the analysis. A summary table reporting reasons for exclusion will be provided.

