7.3 Descriptive statistics

Categorical variables will be described by means of absolute and relative frequencies, while continuous variables by means of mean, standard deviation, quartiles, min and max. Analyses will consider data collected at variable observational points, according to clinical practice and clinical judgement. In order to summarize data by time point the nearest available evaluation measurement will be considered (acceptable range).

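### The plan asks about change within people but specifies only available-case summaries at each visit; if loss is related to risk, the series can move although nobody changes

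*Protocol*

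**What the plan says.** Section 3.1 of the protocol sets the comparison: "Subjects who are included in the PrEP arm will act as their own controls regarding possible changes in psychological and sexual health". Section 3.3 repeats it for sexual health and quality of life, and Section 1.1 makes the impact on psychological and sexual health the main objective.

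The analysis is descriptive: frequencies for categorical variables; mean, SD, quartiles and range for continuous ones (Section 7.3). The same section says "Analyses will consider data collected at variable observational points, according to clinical practice and clinical judgement", and each time point takes the nearest available measurement. On missing data, Section 7.4 says "Subjects missing data values will not be excluded from the analysis, but their data will not be replaced", and adds that "frequency of missing data will be given for all analysed variables". The analysis set is given in Section 7.2: "Data will be described on enrolled subjects undergoing PrEP treatment".

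On visits, Section 4.1 has week 4, week 12 and "thereafter every 3 months during the PrEP treatment for 24 months". The protocol outline instead counts three-monthly visits from PrEP initiation over the next 24 months, and Table 1 puts the end-of-study visit 24 months after treatment start.

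Section 7.1 defers detail to a separate SAP. The SAP supplied repeats Sections 7.1 to 7.4 and adds no method.

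**The concern.** An own-control question is about the same people before and after. A row of by-visit summaries of whoever has a value answers a different one: what the group seen at that visit looks like. The two agree only if the people seen later resemble those who started.

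The text gives reason to doubt that they will. PrEP is offered because of risk (Section 3.1). Section 4.1 ties visits to PrEP treatment, Section 7.2 ties the analysis set to it, and people who seroconvert are transferred out. Table 1 also has assessments captured only if they are conducted. Being observed may therefore depend on the behaviour being measured.

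At stake is the reading of the main objective. A drift in partner numbers, condom use or quality of life between baseline and month 24 could be taken for an effect of PrEP when part of it reflects who is still attending. A by-visit STI series would be open to the same misreading.

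**Working it through.** **Nothing to reproduce.** The protocol outline gives the sample size as "Not applicable". No dropout rate, STI positivity or expected behaviour level is stated. All inputs below are assumptions, chosen so that no person's risk changes.

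**Inputs**
- Each person has a constant probability of a positive screen, with log-odds normally distributed (mean -2.2, SD 1). Numerical integration on either side of the median gives mean positivity L = 5.41% in the lower-risk half and H = 21.30% in the higher-risk half.
- Baseline B = (L + H)/2 = (5.41 + 21.30)/2 = 13.36%, or 13.4%.
- Visits: 24/3 = 8. Loss per visit d is 3% in one half and 6%, 8% or 10% in the other.

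**Formulae**
- Retention in a half: r = (1 - d)^8, which is 0.784 at 3%, 0.610 at 6%, 0.513 at 8% and 0.430 at 10%.
- Month-24 positivity among those seen: M = (r_L × L + r_H × H)/(r_L + r_H).

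**Example.** Lower-risk half at 6%, higher-risk half at 3%: M = (0.610 × 5.41 + 0.784 × 21.30)/(0.610 + 0.784) = (3.30 + 16.70)/1.394 = 14.35%. Relative to B this is 14.35/13.36 = 1.074.

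| Loss per visit, lower / higher risk | Overall retention | Month 24 among those seen | Difference, points | Relative shift |
|---|---|---|---|---|
| 5% / 5% | 66% | 13.4% | 0.0 | 0% |
| 6% / 3% | 70% | 14.3% | +1.0 | +7% |
| 8% / 3% | 65% | 15.0% | +1.7 | +12% |
| 10% / 3% | 61% | 15.7% | +2.3 | +17% |
| 3% / 6% | 70% | 12.4% | -1.0 | -7% |
| 3% / 8% | 65% | 11.7% | -1.7 | -12% |
| 3% / 10% | 61% | 11.0% | -2.3 | -17% |

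**A coarser check.** Take two equal strata with constant positivity of 30% and 10%, so B = 20.0%.
- Total loss of 20% (high) and 40% (low): (0.5 × 0.8 × 30 + 0.5 × 0.6 × 10)/0.7 = 15/0.7 = 21.4%.
- Reversed: (0.5 × 0.6 × 30 + 0.5 × 0.8 × 10)/0.7 = 13/0.7 = 18.6%.
- Equal 30% loss: 20.0%.
- Mean partner counts of 15 and 5 (baseline 10.0) give 10.7 and 9.3 under the same two unequal patterns, so counts are affected like percentages.

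**Does a same-subject baseline help?** With constant individual risk, the baseline of those retained has the same expected value as their month-24 figure, so the expected paired change is zero. In a simulation of 400,000 people with the two strata and five dropout patterns, the paired change lay between -0.21 and -0.05 points. The comparison with everyone's baseline ranged from -2.96 to +2.63 points.

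**The case against.** The strongest reply is that this is a descriptive study and the plan nowhere commits to the misleading comparison. Much of that stands, and four stronger readings should be resisted.

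- A reader might infer that the trends will move. They move only if loss is related to risk. Equal loss gives no shift, and the sign reverses if higher-risk people leave faster.
- A reader might infer that follow-up is to be set against the full baseline group. No section says so. The own-control wording would allow a paired summary; the plan simply does not specify one.
- A reader might infer that people leave because their risk has fallen, or that visits cease when PrEP does. The first is stated nowhere. On the second, Section 4.1 points that way, but the outline and Table 1 time visits from PrEP start without requiring continued use.
- A reader might take Section 7.4 to keep people without a result in the denominator, so that percentages fall as follow-up is lost. The natural meaning is that someone lacking one value still contributes the others, and missing frequencies are reported separately. No false fall should be attributed to the plan on that basis.

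It is also fair to say that the named STI comparator is national surveillance (Section 3.3), not the cohort's own baseline, and that describing people still on PrEP fits Section 7.2. Nor is leaving values unreplaced a fault in itself.

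What remains is that reporting missingness shows how far the group shrinks but not whether it has changed in composition, and the own-control objective has no matching analysis.

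**Conclusion.** The point holds in conditional form. The only analysis specified is a set of available-case cross-sections, while the main question is within-person change. If loss is related to risk, which the text makes plausible but does not establish, behaviour, quality-of-life and any by-visit STI series can move with no individual change.

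On the assumed inputs, the shift in month-24 positivity is about 7-17% in relative terms (1.0 to 2.3 points on 13.4%) in either direction. These figures rest on an assumed spread of risk and assumed differential loss. Neither the size nor the direction in this cohort can be derived from the documents. No hypothesis test or sample-size calculation is affected; what is affected is interpretation. The change is worth making before the analysis, because the remedy is cheap and uses data already collected.

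**What to change.** In Sections 7.3 and 7.4 of the SAP:

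1. State that the denominator of every by-visit percentage is the number of people with a result at that visit.
2. Beside each follow-up value, show the baseline value of the same people and the within-person change.
3. Estimate the time course of behaviour and quality of life, and of by-visit STI positivity if reported, with a repeated-measures model using all observed visits. A likelihood-based mixed model suits this: logistic for STI positivity, a count model for partners. It relies on loss being explained by the observed data, so baseline risk criterion, age and regimen belong among the covariates. State whether visits after stopping PrEP contribute.
4. Compare the baseline characteristics of leavers and stayers.

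A sensitivity analysis weighted by the probability of still attending is optional.

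The cost is SAP wording and modest programming. One limitation should be stated: the same-subject contrast describes only those retained, so it should be read together with the model.

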7.5 Data Collection / Case Report Forms

Data will be collected using an electronic data capture (EDC) solution. Electronic Case report forms (eCRFs) will be utilised for recording data from each subject meeting the eligibility criteria but will not be completed for subjects who fail to meet eligibility criteria. The eCRF system, VieDoc™, will be available on an internet portal accessible through any standard computer with internet access. A personal log-in will be provided for all responsible personnel to allow for an audit trail relating to the study data to be maintained.

For the subject questionnaire at 3 months follow-up and the subject diary there will be an option to complete these electronically through the app ViedocMe™ on a smart phone.

The data in the eCRFs should be consistent with the relevant source documents. The Investigator will sign the designated signature fields of the eCRF data entry screens to confirm that the information on each screen is accurate and complete. All data must be stored in an unidentifiable form treated with strict confidentiality in accordance with applicable data protection regulations.

7.6 Data Management

Data will be transmitted electronically into the web based EDC system. Upon receipt, data will be coded according to pre-specified dictionaries. The handling of data, including data quality control, will comply with all applicable regulatory guidelines.

8 REGULATORY AND ADMINISTRATIVE PROCEDURES

8.1 Institutional Review

The study will be conducted in accordance with the Fortaleza, 2013 amendment to the Declaration of Helsinki 1964.

The Protocol and the Patient Information Sheet / Informed Consent Form will be approved by the relevant Competent Authorities and Ethics Committees, and possibly other public bodies according to local requirements before commencement. If a protocol amendment is necessary, this will be prepared with the agreement of the Principal Investigator, and signed by the relevant parties. If the amendment is considered to be substantial, it will be submitted to the Competent Authorities and Ethics Committees, and possibly other public bodies according to local requirements for review and approval. The protocol amendment will not be implemented before the required approvals are obtained. Minor amendments which do not affect the safety or physical or mental integrity of the clinical trial participants or the scientific value of the trial (i.e. non-substantial amendments) will not be submitted to Competent Authorities or Ethics Committees.

8.2 Patient Information / Informed Consent

The Investigator is responsible for giving the study subject full and adequate verbal and written information about the nature, purpose, possible risk and benefit of the study. Study subjects must also be notified that they are free to withdraw from the study at any time. The subjects should have reasonable time to read and understand the information before signing. The Investigator is responsible for obtaining signed informed consent from all subjects before including the subject in any study related procedures.

A signed copy of the patient information and of the Informed Consent Form in local language, will be given to the subjects, [Appendix 12.1](#).

8.3 Subject Confidentiality

The Investigator must ensure that subject's confidentiality will be maintained. eCRFs should only identify subjects by their initials and study number. The Investigator should keep a separate log of subject codes and names. Documents not for submission to the Sponsor, e.g., subject's completed Consent Forms, should be retained by the Investigator in strict confidence.

The Investigator is required to record primary efficacy and safety data, concomitant medication and subject progress in the subject's file/notes/medical record.

8.4 Subject Treatment Plan

It will be possible for the subject to continue with the PrEP treatment after end of the study. Subject withdrawing their consent will be offered to continue with the PrEP treatment independently of their study participation.

8.5 GCP

The study will be managed and conducted according to the latest International Conference on Harmonisation (ICH) guidelines for Good Clinical Practice (GCP). A copy of these guidelines can be found in the Investigator Site File (ISF).

8.6 Record Retention

eCRFs and all medical records upon which the eCRF are based (source data) must be kept for at least 15 years after completion of the study. Image carriers or other data carriers may be used for this purpose. The documentation should be easily retrievable and readable during the entire archiving duration.

8.7 Quality Assurance

During or after the study is completed, sponsor representatives or regulatory authorities may wish to carry out an audit or an inspection. These representatives must have the access to all study data and subject source data.

8.8 Insurance and Liability

Liability for IMP-induced injury will be according to local requirements. The sponsor will indemnify the Investigator in accordance to national regulations.

8.9 End of Trial

The end of the trial is defined as the last visit of the last subject included in the trial. Within 90 days of the end of the trial, the Sponsor will notify Competent Authorities and Ethics Committees the regular termination of the study as required according to national law and regulations.

8.10 Study Report

A study report SR will be prepared covering clinical and statistical aspects and summarising all findings of the clinical study. The content has to be treated as strictly confidential. The study report will be sent to the Investigators, the Competent Authorities and Ethics Committees according to local requirements.

8.11 Publication and Data Rights

It is envisaged that the findings of the study will, in due course and by mutual agreement, be published in a scientific journal and/or presented at a scientific meeting

The published international guidelines for authorship (International Committee of Medical Journal Editors, 1997) will be adhered to; i.e. 'All persons designated as authors should qualify for authorship. Each author should have participated sufficiently in the work to take public responsibility for the content.'

Authorship credit will therefore be based only on substantial contributions to 1) conception and design, or analysis and interpretation of data; and to 2) drafting the article or revising it critically for important intellectual content; and on 3) final approval of the version to be published. Conditions 1), 2) and 3) must all be met. Participation solely in acquisition of funding or the collation of data does not justify authorship. General supervision of the research group is not sufficient for authorship. It is intended that information on what each author has contributed will be published.

It is emphasised however, that only those who entirely meet the above mentioned criteria will be listed as authors.

12 APPENDICES

12.1 Patient Information Sheet /Informed Consent Form

12.2 Questionnaires

## PROTOCOL OUTLINE

Working title		Implementation of pre-exposure prophylaxis (PrEP) in subjects at particular high risk for human immunodeficiency virus (HIV) acquisition - an evaluation study.
Study objectives		
 
• Assess the impact of PrEP on the sexual and psychological health of PrEP users
 
• Incidence of sexually transmitted infections (STIs) in PrEP users compared to those not taking PrEP
 
• Assessment of drug compliance
 
• Incidence of HIV seroconversion despite PrEP
 
• Frequency and development of drug resistance in subjects who HIV-seroconvert (if any)
 

Selection criteria (abbreviated)	Inclusion	
 
1. Male, female or transgender persons aged <math>\geq 18</math> years who are offered or have started PrEP in routine clinical practice, and 2, 3, 4, 5, 6 or 7 (below).
 
2. Men who have sex with men (MSM) and transgender persons;               
 
a. who have had unprotected anal sex with two or more partners during the last six months and/or
 
b. who have had bacterial sexually transmittable infection(s) during the last twelve months and/or
 
c. who have used post-exposure prophylaxis(PEP) during the last twelve months and/or
 
d. who use recreational drugs when having sex
 
 
 
3. Indication for PrEP is present according to the assessment of the health care provider
 
4. Men and women who are at high risk of HIV according to their sexual practices
 
5. HIV-negative partner of a HIV-positive person not yet virologically suppressed by antiretroviral therapy (ART)
 
6. Sex workers with inconsistent condom use
 
7. Persons with inconsistent condom use with sexual partners in / from countries with a high prevalence of HIV (COHP)
 

	Exclusion	
 
1. HIV positive subjects
 
2. Subjects who cannot take Truvada® due to contraindications
 

	Control group	
 
1. Enrolled patients will be regarded as their own control when it comes to their sexual health and quality of life reported for period prior to inclusion in the study.
 
2. Subjects diagnosed with HIV in general clinical practice and referred to the out-patient clinic at the Dept. of Infectious Diseases, OUS.
 
3. Frequency of STI reported to the National Institute of Public Health (MSIS) will be compared with the frequency of STIs in the study cohort.
 

Methods & procedures		
PrEP assessment occurs on designated clinic days at The Olafia clinic and will be performed by a team of doctors and nurses specifically trained in PrEP assessment. Persons may be self-referred or referred from other health providers for PrEP assessment. At other sites this will be organized according to the local resources.
 
Subjects will be provided with written and oral information about the study and invited to sign an informed consent form. Subjects not consenting to participation in the study will still be offered PrEP (if indicated) and follow up according to national (NFIM) and local (Olafiaklinikken) guidelines.
 
Subjects who sign the consent form will go through an enrolment procedure to ensure that the PrEP treatment is indicated according to inclusion/exclusion criteria (based on national and local guidelines). Study participants will be asked to complete a questionnaire with detailed information on demographics, medical history, sexual behaviour the last 6 months, perception of HIV risk at the last condomless sex, risk management strategies, personal history of STIs, HIV& STI testing frequency and drug/alcohol use.

		
Subject will be screened for the following STIs during the enrolment visit; HIV, syphilis, hepatitis A/B/C, Chlamydia trachomatis, Neisseria gonorrhoea, and Mycoplasma genitalium.
 
Participants will be asked to return approximately one week later to discuss their HIV result and whether they wish to proceed with initiation of PrEP.
 
The decision regarding initiation of continuous or intermittent PrEP is based on a discussion with the subject and study team (doctor/nurse), subjects' personal preference, medical considerations and whether the expected use will surpass more than 15-20 tablets of Truvada per month.
 
HIV testing will be repeated at 2, 4 and 8 weeks from the most recent high risk exposure (for HIV acquisition) prior to initiation of PrEP. Thereafter participants are requested to visit the clinic every 3 months from PrEP initiation (for the next 24 months) for HIV & STI testing, evaluation of compliance (blood test for drug monitoring in continuous PrEP arm, drug diaries in both continuous and intermittent PrEP arms), assessment of clinical and/or biochemical adverse reactions and quality of life and sexual behaviour assessment. Subjects will be asked to answer the same questions regarding sexual behaviour and quality of life at follow up visits as at inclusion study visit.

Statistics	Sample size	Not applicable
	Methods	Categorical variables will be described by means of absolute and relative frequencies, while continuous variables by means of mean, standard deviation, quartiles, min and max.

